#### **Objectives:**

**Primary objective:** To assess the safety and feasibility of delivering 15 fractions of SIB radiotherapy to the breast in patients at risk for developing cutaneous toxicity.

#### **Primary Outcome Measure:**

- Cutaneous Toxicity Rate Cutaneous toxicity rate will be assessed by the National Cancer Institute Common Toxicity Criteria (NCI-CTC) v 3. grading scale.
- 1. Rate of 20% or greater increase in arm lymphedema (compared to baseline arm measurements) will be assessed Among breast cancer patients receiving regional nodal irradiation
- 2. Rate of Grade 3 brachial plexopathy will be assessed among breast cancer patients receiving regional nodal irradiation by RTOG and LENT/SOMA scales

### Secondary Outcome Measures:

- 1. Rate of cutaneous toxicity, as measured by changes in cutaneous measurements, acquired vis ultrasound tissue characterizations (UTC)
- 2. Local control will also be assessed through routine physical examination, annual screening mammograms, ultrasound, and biopsy to confirm local recurrence.
- Blood will be analyzed for biomarkers and inflammatory markers including(tumor necrosis factor (TNF)-alpha, soluble TNF receptor 2 (sTNFR2), interleukin (IL)-6, IL-1ra, and C - reactive protein (CRP) as well as genetic factors to determine if they are associated with development of cutaneous toxicity.
- 4. Change in Multidimensional Fatigue Inventory (MFI) Score

[Time Frame: Baseline, End of Follow Up (Up to 18 months)] [Safety Issue: No]

The Multidimensional Fatigue Inventory (MFI) is a 20-item self-report instrument designed to measure fatigue. Scores range from 20 to 100. The higher the score, the more fatigued.

5. Change in Pittsburgh Sleep Quality Index (PSQI) Score

[Time Frame: Baseline, End of Follow Up (Up to 18 months)] [Safety Issue: No]

The PSQI is a self-rated questionnaire which assesses sleep quality and disturbances over a 1-month time interval. Scores range from 0 to 21. A score of less than or equal to 5 is associated with good sleep quality. A score greater than 5 is associated with poor sleep quality.

6. Change in Perceived Stress Scale (PSS) Score

[Time Frame: Baseline, End of Follow Up (Up to 18 months)] [Safety Issue: No]

The PSS is a self-reported instrument used to measure the perception of stress. Scores range from 0 to 40. Score of 20 or higher are considered high stress.

7. Change in Patient Reported Outcomes Measurement Information System (PROMIS) Fatigue Short Form Score

[Time Frame: Baseline, End of Follow Up (Up to 18 months)] [Safety Issue: No]

The PROMIS Fatigue questionnaire is a self-report tool used to evaluate frequency, duration, and intensity of fatigue over the past seven days. Scores range from 7 to 35. The higher the score, the more fatigue.

8. Change in an Inventory of Depressive Symptomatology-Self Reported (IDS-SR) score

[Time Frame: Baseline, End of Follow Up (Up to 18 months)] [Safety Issue: No]

The IDS-SR is a self-reported measure in which participants rate the frequency of depression symptoms within the past seven days. Scores range from 0 to 84, with higher score reflecting greater severity of depressive symptoms.

9. Change in Short Form-36 (SF-36) Health Survey Score

[Time Frame: Baseline, End of Follow Up (Up to 18 months)] [Safety Issue: No]

The SF-36 is a self-reported survey of health status. Scores range from 0 to 100. Lower scores indicate disability. The higher the score, the less disability.

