Seeking to shorten the treatment course further and improve convenience and treatment adherence, we propose to build upon our experience and the level I evidence advocating for hypofractionation in 15 days of treatment. Our proposed study will utilize the SIB technique with the whole breast treated to 40 Gy in 15 fractions and the cavity boosted simultaneously to 48 Gy in 15 fractions. Only one previous study has examined the feasibility of a similar fractionation with the whole breast treated to 40.5 Gy in 15 fractions, while the cavity is treated to 48 Gy.(20) At 1 year median follow-up time, 67% of patients had developed reversible grade 1-2 skin dermatitis and only 1 of 91 patients had recurred locoregionally.(20) However, only 1/3 of patients received chemotherapy and less than a quarter had large breast size. The majority of patients were over the age of 50 and 87% were Caucasian.(20) No study has examined the feasibility of a 15-day hypofractionated SIB XRT regimen in women at high risk for cutaneous toxicity (e.g. women below the age of 50, African American, and/or treated with chemotherapy). The unique patient population served by Emory will enable a study of SIB XRT given 12/13/2016

over 15 treatments. Quality of life measures (e.g. Multidimensional Fatigue inventory (MFI)[18], the Pittsburgh Sleep Quality Index (PSQI) [19], the perceived stress scale (PSS)[20], the Inventory of Depressive Symptomalogy-Self Reported (IDS-SR)[21], the Short-Form Health Survey (SF-36)(25) and the Godin Leisure Time Questionnaire (GLTEQ)(26)) which have been validated in multiple populations, will also be assessed in these patients to determine if 15 days of treatment is feasible.

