### Data Collection:

Cutaneous toxicity will be assessed at baseline, fraction 15 of XRT and 2 - 5 weeks, 7 - 12 weeks, and 12 – 18 months post XRT by objective ultrasound measurements (UTC). Photographs of the treated breast or chest wall as well as the contralateral breast will also be taken. Documentation of the UTC and photographs will be kept in electronic format for reference. For each visit after the baseline (after treatment has begun), cutaneous toxicity will be assessed by a clinician. Participants will be seen by the investigator in follow up at the third and/or fourth visits and at the fifth visit and an investigator dictation will be performed.

Patients who have had a mastectomy and plan for permanent breast reconstructive surgery after radiation will be assessed within one month of their permanent reconstructive surgery and 5 - 7 months following their surgery using the same procedures as described above. It is highly variable as to when reconstruction will occur. If these time points do not fall within the time frame for the regular study visits, additional study visits will be added for these patients.

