Participants will also be asked to complete the Multidimensional Fatigue inventory (MFI)[18], the Pittsburgh Sleep Quality Index (PSQI) [19], the perceived stress scale (PSS)[20], the Inventory of Depressive Symptomalogy-Self Reported (IDS-SR)[21], the PROMIS Fatigue Short form [28], the MOS-item Short-Form health survey (SF-36)(25) and the Godin Leisure-Time Exercise Questionnaire (GLTEQ)(26) to assess levels of fatigue, sleep, stress, and depression at the above time points. These surveys take approximately 15 minutes to complete. Patients who are simultaneously enrolled on the Fatique in Breast Cancer Patients Undergoing Treatment (IRB00028295) may have survey visit assessments completed prior to baseline visit, as they are completing the same assessments for both studies. These surveys will be used for data purposes in lieu of having the patient complete the same paperwork twice. At each visit, patients will be asked to rate their fatigue level and breast pain on a scale of 0-10, 0 being none and 10 being extreme. They will be asked to rate how happy they are with the look of their breast on a scale of 0-10, 0 being not happy and 10 very happy. They will be asked to rate how different their radiated breast is from their non-radiated breast on a scale of 0 - 10, 0 being no difference and 10 being completely different. The patient's self-report of fatigue at these visits will be used to assess the grade of their fatigue. In addition, patients will complete the LENT SOMA [27] scale patient questionnaire at all study timepoints to address pain within the breast. The objective LENT SOMA questionnaire Part 3 will be completed by a study clinician or trained nurse at each visit after baseline.

Blood will be drawn under fasting conditions at visits corresponding to cutaneous toxicity assessments. The blood will be analyzed for inflammatory markers (tumor necrosis factor (TNF)-alpha, soluble TNF receptor 2 (sTNFR2), interleukin (IL)-6, IL-1ra, and C - reactive protein (CRP) as well as genetic factors to determine if they are associated with development of cutaneous toxicity.

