Information regarding disease characteristics (including stage, tumor size, grade), patient demographics (including age, race, co-morbidities, social history, body mass index), systemic treatment (including hormone therapy, systemic therapy), surgical treatment, radiation treatment, and clinical outcomes (local control, distant metastasis, survival, and treatment complications) will be collected and recorded.

Patients may also be asked to participate in a long term assessment between 1 and 10 years where they will complete the same study procedures as outlined above. Patients will be compensated \$50.00 for completing this visit.

A follow up phone survey will be taken between 18 months and 10 years after treatment. Using the same scales as in the study visits, the patients will be asked to rate their fatigue level, breast pain, how happy they are with the look of their breast and how different their radiated breast is from their non-radiated breast. They will also be asked if they are on any hormonal treatment for breast cancer and if so, the date they started. We will obtain verbal consent for this survey from patients who completed this study before the follow up phone survey was originally approved on 9/24/2013.

Assuming 10% of patients dropout, 53 patients requiring breast only radiation will be enrolled (2-3 patients per month) to yield a total of 50 patients.

An additional 33 patients requiring regional nodal irradiation and breast or chest wall radiation will be enrolled. Assuming 10% of patients dropout, 33 patients of these patients will be enrolled (2-3 patients per month) to yield a total of 30 patients receiving regional nodal irradiation and breast or chest wall radiation.

In patients undergoing regional nodal irradiation, arm measurements will be taken of the ipsilateral and contralateral upper extremity at baseline, 7 - 12 weeks, and 12 – 18 months post XRT by a licensed lymphedema therapist or study staff trained by a licensed lymphedema therapist. These patients will also be assessed for brachial plexopathy using RTOG grading toxicity, LENT/SOMA grading toxicity, and a modified version of a validated questionnaire to assess symptoms of brachial plexopathy at baseline and 7 - 12 weeks, and 12 – 18 months post XRT.[24] If a patient develops RTOG or LENT/SOMA Grade 3 toxicity, an objective measurement (MRI and/or nerve conduction studies) of brachial plexopathy will be employed.

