### 10. Change in Godin Leisure-Time Exercise Questionnaire (GLTEQ) Score

[Time Frame: Baseline, End of Follow Up (Up to 18 months)] [Safety Issue: No]

The GLTEQ is a self-reported questionnaire used to measure usual leisure-time exercise habits during a typical seven day period. A score of 24 or more indicates active and substantial exercise benefits. A score of 23 units or less indicates insufficiently active and less substantial exercise benefits.

11. Change in Lent Soma Scale Patient Questionnaire Score

[Time Frame: Baseline, End of Follow Up (Up to 18 months)] [Safety Issue: No]

The Lent Soma questionnaire is a self-reported measure of pain. Scores range from 0 to 9. The higher the score, the more pain reported.

12. Change in Fatigue Level

[Time Frame: Baseline, End of Follow Up (Up to 18 months)] [Safety Issue: No]

Participants will be asked to rate their fatigue level on a study specific scale from 0 to 10 where 0 represents no fatigue, and 10 represents the most extreme fatigue.

13. Change in Breast Pain Level

[Time Frame: Baseline, End of Follow Up (Up to 18 months)] [Safety Issue: No]

Participants will be asked to rate their breast pain level on a study specific scale from 0 to 10 where 0 represents no pain, and 10 represents the most extreme pain.

14. Change in Breast Appearance Satisfaction Score

[Time Frame: Baseline, End of Follow Up (Up to 18 months)] [Safety Issue: No]

Participants will be asked to rate the look of their breast on a study specific scale from 0 to 10 where 0 represents not happy, and 10 represents very happy.

15. Difference in Radiated Breast Appearance Score

[Time Frame: Baseline, End of Follow Up (Up to 18 months)] [Safety Issue: No]

Participants will be asked to rate how different the look of their radiated breast is compared to their non-radiated breast on a study specific scale from 0 to 10 where 0 represents no difference, and 10 represents completely different.

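### All twelve patient-reported outcomes compare baseline with an undefined end of follow-up, so their definitions leave out the on-treatment and early recovery scores that the protocol collects

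*Protocol*

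**What the plan says.** **Outcome definition.** In the protocol's Secondary Outcome Measures, items 4 to 15 are MFI, PSQI, PSS, PROMIS Fatigue, IDS-SR, SF-36, GLTEQ, the LENT SOMA patient questionnaire and four 0-10 ratings. Each has the same time frame, "Time Frame: Baseline, End of Follow Up (Up to 18 months". Items 4 to 14 are titled as changes. Item 15 is titled "Difference in Radiated Breast Appearance Score" and compares the two breasts.

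**Collection.** The Data Collection section gives the visits: "Cutaneous toxicity will be assessed at baseline, fraction 15 of XRT and 2 - 5 weeks, 7 - 12 weeks", and then 12-18 months after radiotherapy. The questionnaires are completed "to assess levels of fatigue, sleep, stress, and depression at the above time points". For the ratings, "At each visit, patients will be asked to rate their fatigue level and breast pain on a scale of 0-10", and the two appearance ratings follow in the same paragraph. The LENT SOMA "scale patient questionnaire at all study timepoints to address pain within the breast".

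**Purpose.** The Background names MFI, PSQI, PSS, IDS-SR, SF-36 and GLTEQ and says that they "will also be assessed in these patients to determine if 15 days of treatment is feasible".

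**SAP.** The Outcome and definition section lists skin thickening ratio at baseline, at 1 year and as a change, plus three time-to-event outcomes. It lists no patient-reported outcome. The Statistical Analysis section names no repeated-measures method and no rule for a missing final visit.

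**The concern.** A 15-fraction course is tolerated or not at its end and in the weeks that follow. The protocol places assessments there, then defines the outcomes so that those assessments do not enter them. A contrast between baseline and 12-18 months describes late recovery, together with whatever else has happened in the intervening year.

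The recall periods in Secondary Outcome Measures sharpen this. PROMIS Fatigue and IDS-SR look back seven days and PSQI looks back one month. A score taken a year or more after radiotherapy cannot describe how the patient felt during it.

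At stake is a conclusion that the regimen left fatigue, sleep, mood or pain unchanged when the acute effect was never part of the outcome. The undefined end point adds a second problem: two analysts could compute different outcomes from the same data.

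**Working it through.** The documents give no sample size, effect size, SD or power for any patient-reported outcome, so there is no planned figure to reproduce. The check compares definition with schedule and then sizes the two readings of the time frame.

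**1. Count.** Items 4 to 15 make 15 − 4 + 1 = 12 outcomes, of 15 secondary outcomes.

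**2. Schedule against definition.**

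| Assessment | Collected | Named in items 4-15 |
|---|---|---|
| Baseline | yes | yes |
| Fraction 15 | yes | no |
| 2-5 weeks | yes | no |
| 7-12 weeks | yes | no |
| 12-18 months | yes | only if this is what end of follow-up means |

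For a patient who completes the schedule, the definitions use 2 of 5 assessments and omit 3 of the 4 after baseline.

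**3. Is the end point identifiable?** The 18-month limit fits the 12-18 month visit. It also fits each patient's last score up to that limit. Data Collection adds visits around reconstruction at variable times, and an optional long-term assessment between 1 and 10 years that can fall before 18 months. Nothing in either document chooses between these.

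**4. What each reading shows of an acute change.** Let A be the mean change at the acute visit, L the mean change at 12-18 months, and d the share of patients whose last score is the acute one.

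- Fixed-visit reading: outcome = L.
- Last-score reading: outcome = d × A + (1 − d) × L.

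Assume full resolution (L = 0) and that every dropout leaves at an acute visit. The fixed-visit reading then gives 0. The last-score reading gives d × A.

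For d, Data Collection states: "Assuming 10% of patients dropout, 53 patients requiring breast only radiation will be enrolled", to yield 50, and 33 to yield 30. The headcounts themselves imply 3/53 = 5.7% and 3/33 = 9.1%. The 30% row and both values of A are assumptions.

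| d | A = 0.5 SD | A = 1.0 SD |
|---|---|---|
| 5.7% | 0.03 SD | 0.06 SD |
| 9.1% | 0.05 SD | 0.09 SD |
| 10% | 0.05 SD | 0.10 SD |
| 30% | 0.15 SD | 0.30 SD |

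At 10% dropout the stated outcome therefore shows between none and one tenth of a resolving acute change. If part of the change persists (L above 0), the outcome shows at least that part, but still cannot separate it from the acute effect.

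**The case against.** The strongest reply is that these are secondary outcomes with a loosely worded label. The last scheduled visit is at 12-18 months, so the time frame most naturally means that visit. Severe acute skin toxicity is covered by the primary NCI-CTC outcome and by continuous monitoring. The protocol does collect scores at fraction 15 and at both early visits.

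Much of this stands, and it rules out four stronger readings that a reader might infer:

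- *That acute scores from dropouts are mixed into a late endpoint.* No carry-forward rule appears in either document. Enrolment is inflated so that a target number remains after dropout, which suggests that dropouts are lost from the evaluable set and not scored early. Under that reading the mixing is zero.
- *That the early scores have no use at all.* Data Collection says self-reported fatigue at the visits is used to grade fatigue. That is one stated use, for one of the twelve measures.
- *That all twelve measures were meant to judge the 15-day course.* The Background says so for six. It does not say so for PROMIS Fatigue, LENT SOMA or the four ratings, and the two appearance ratings are reasonable late outcomes.
- *That the trial skips the treatment period.* Only the outcome definitions do.

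The reply does not meet the main point. Skin grading does not measure fatigue, sleep, stress or mood. Choosing the fixed-visit reading removes the mixing but leaves a resolving acute change wholly outside the outcome. The SAP does not restore it. For ultrasound, the Correlative Studies paragraph expressly values all five time points for following development and resolution; no such statement covers the patient-reported measures.

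**Conclusion.** The concern holds in this form: the definitions of all twelve patient-reported outcomes omit three of the four post-baseline assessments and do not say which visit ends follow-up. For the six instruments tied to feasibility of the 15-day course, the stated contrast does not address that purpose.

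The size depends on how far acute effects resolve, which the documents do not give for these scales. Under full resolution the outcome shows nothing of the acute change on the fixed-visit reading. On the last-score reading it shows about 10% of it at the planned dropout, or 0.05 to 0.10 SD for acute changes of 0.5 to 1.0 SD. The loss of the acute contrast is the main defect under either reading. Mixing of early and late scores is a small risk created by the wording.

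The absence of every patient-reported outcome from the SAP is a wider gap, and it means that the SAP does not correct this one. The change should be made, but it concerns secondary outcomes and does not affect the primary toxicity assessment.

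**What to change.** - In items 4 to 14, replace the time frame with change from baseline at each scheduled visit. In item 15, use the score at each visit.
- Name fraction 15 and 2-5 weeks as the acute contrasts, and tie the late contrast to the 12-18 month visit.
- For PSQI, note that one-month recall at fraction 15 reaches back before a three-week course began, so that contrast is partly pre-treatment.
- Add the twelve scales to the SAP. Fit one repeated-measures mixed model per scale, with visit as a factor and each score entered at the visit where it was taken. Carry nothing forward. State the missing-at-random assumption and report the number assessed at each visit.

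**Cost.** The protocol already schedules these assessments, so no new data collection is needed. Three named contrasts on twelve scales give 3 × 12 = 36 estimates, and the plan has no multiplicity control for them. Report them descriptively with confidence intervals. The SAP is dated April 2021, is written in the past tense and already counts 75 included cases, so the addition must be dated and labelled post hoc.

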### 10. Change in Godin Leisure-Time Exercise Questionnaire (GLTEQ) Score

[Time Frame: Baseline, End of Follow Up (Up to 18 months)] [Safety Issue: No]

The GLTEQ is a self-reported questionnaire used to measure usual leisure-time exercise habits during a typical seven day period. A score of 24 or more indicates active and substantial exercise benefits. A score of 23 units or less indicates insufficiently active and less substantial exercise benefits.

11. Change in Lent Soma Scale Patient Questionnaire Score

[Time Frame: Baseline, End of Follow Up (Up to 18 months)] [Safety Issue: No]

The Lent Soma questionnaire is a self-reported measure of pain. Scores range from 0 to 9. The higher the score, the more pain reported.

12. Change in Fatigue Level

[Time Frame: Baseline, End of Follow Up (Up to 18 months)] [Safety Issue: No]

Participants will be asked to rate their fatigue level on a study specific scale from 0 to 10 where 0 represents no fatigue, and 10 represents the most extreme fatigue.

13. Change in Breast Pain Level

[Time Frame: Baseline, End of Follow Up (Up to 18 months)] [Safety Issue: No]

Participants will be asked to rate their breast pain level on a study specific scale from 0 to 10 where 0 represents no pain, and 10 represents the most extreme pain.

14. Change in Breast Appearance Satisfaction Score

[Time Frame: Baseline, End of Follow Up (Up to 18 months)] [Safety Issue: No]

Participants will be asked to rate the look of their breast on a study specific scale from 0 to 10 where 0 represents not happy, and 10 represents very happy.

15. Difference in Radiated Breast Appearance Score

[Time Frame: Baseline, End of Follow Up (Up to 18 months)] [Safety Issue: No]

Participants will be asked to rate how different the look of their radiated breast is compared to their non-radiated breast on a study specific scale from 0 to 10 where 0 represents no difference, and 10 represents completely different.

### Monitoring Plan for Severe Adverse Events:

We hypothesize that a maximum of 20% of patients might experience severe acute skin side effects defined as NCI-CTC Grade 3. This corresponds to symptoms interfering with activities of daily life. A Data Safety and Monitoring Board (DSMB) will monitor patient outcomes and suspend the protocol in the event that more than 16 of 80 patients demonstrate severe acute skin toxicity. During the study, the patients will be monitored continuously throughout the study such that if at any time during the study the upper limit of the number of patients developing Grade 3 toxicity exceed what is listed in the table below, the trial will be discontinued. With a 10% dropout rate, a total sample size of 83 patients was calculated to effectively test our hypothesis. For patients not requiring regional nodal irradiation, we will only collect adverse events related to skin toxicity, lung toxicity and heart toxicity. We will not report grade 1-2 radiation dermatitis as adverse events because most patients will at least have gr 1 dermatitis. We will keep a record of toxicity at each visit by collecting the Lent Soma evaluation of

the clinician at each visit after treatment starts. Patient reported fatigue rate will not be collected on the adverse event report, but will also be recorded at each visit

Total Patients	Upper limit of number of patients with toxicity for the trial to continue	Proportion of patients with toxicity if exceed the upper limit	Lower limit of 95% Cl	Upper Limit of 95% CI
3	<3	100%	29%	100%
4	<4	100%	40%	100%
5	<4	80%	28%	99%
6	<4	67%	22%	96%
7	<5	71%	29%	96%
8	<5	63%	24%	91%
9	<5	56%	21%	86%
10	<6	60%	26%	88%
11	<6	55%	23%	93%
12	<6	50%	21%	79%
13-50	<7	>20%	NA	

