will be monitored throughout the study such that if at any time during the study the upper limit of the number of patients receiving regional nodal irradiation developing Grade 3 brachial plexopathy or 20% or greater increase in arm lymphedema exceed the number just described or more than 20% develop grade 3 skin toxicity within the breast or chest wall, the trial will be discontinued to the patients requiring regional nodal irradiation but may remain open to patients who do not require regional nodal irradiation. For patients requiring regional nodal irradiation, we will only collect adverse events related to brachial plexopathy, lymphedema, skin toxicity, lung toxicity, heart toxicity. We will not report grade 1-2 radiation dermatitis as adverse events because most patients will at least have gr 1 dermatitis. We will keep a record of toxicity at each visit by collecting the Lent Soma evaluation of the clinician at each visit after treatment starts. Patient reported fatigue rate will not be collected on the adverse event report, but will also be recorded at each visit.

Stopping rule for monitoring 3 types of toxicities in patients Receiving Regional Nodal Irradiation.

Total Patients	Upper limit of number of patients with Grade 3 brachial plexopathy (<3%)	Upper limit of number of patients with 20% or greater increase in arm lymphedema (<15%)	Upper limit of number of patients with grade 3 skin toxicity within the breast or chest wall (<20%)
3	<2	<3	<3
4	<2	<3	<4
5	<2	<4	<4
6	<2	<4	<4
7	<2	<4	<5
8	<2	<4	<5
9	<2	<5	<5
10	<2	<5	<6
11	<2	<5	<6
12	<2	<5	<6
13-30	<2	<5	<7

(If any one of the 3 stopping rules is met, the trial stops for excessive toxicity.)

**Correlative Studies**: Blood will be analyzed for inflammatory markers (TNF-alpha, soluble sTNFR2, IL-6, IL-1ra, and CRP) to determine if they are associated with development of cutaneous toxicity. By acquiring the objective UTC measurements at 5 time points, the development and resolution of cutaneous toxicity as it relates to time may be further understood.

A description of the Feasibility:

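### The Grade 3 skin stopping table is mislabelled as above 20% for 35 to 50 patients, and the protocol's skin stopping limits do not agree with one another

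*Protocol*

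**What the plan says.** Four statements in the protocol govern stopping for Grade 3 skin toxicity.

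- **Overall limit.** The Monitoring Plan for Severe Adverse Events says: "We hypothesize that a maximum of 20% of patients might experience severe acute skin side effects defined as NCI-CTC Grade 3". It has the DSMB "suspend the protocol in the event that more than 16 of 80 patients demonstrate severe acute skin toxicity".
- **First table.** The same paragraph adds continuous monitoring: if the counts "exceed what is listed in the table below, the trial will be discontinued". The table has one row for each total from 3 to 12, then a single row for 13 to 50. That row requires fewer than 7 events, gives the proportion as above 20%, and prints NA for the confidence interval. The cohort covered is not named.
- **Nodal text.** The section on patients requiring regional nodal irradiation closes that cohort if at any time "more than 20% develop grade 3 skin toxicity within the breast or chest wall", and says the trial "but may remain open to patients who do not require regional nodal irradiation".
- **Nodal table.** Its skin column repeats the first table and ends with fewer than 7 events for 13 to 30 patients. The note below it reads: "If any one of the 3 stopping rules is met, the trial stops for excessive toxicity".

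The Data Collection section plans "53 patients requiring breast only radiation will be enrolled (2-3 patients per month) to yield a total of 50 patients", and a further 33 enrolled to yield 30 nodal patients. The SAP contains no stopping boundary.

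**The concern.** A flat limit of 7 events over totals from 13 to 50 cannot correspond to a proportion above 20% throughout, because 7/n falls as n grows. At the upper end the table orders discontinuation at an observed rate that does not exceed the protocol's own maximum. A stop there could not be read as evidence that toxicity is above 20%.

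The table also sits beside a 16-of-80 limit and, for nodal patients, a percentage rule, with nothing to say how they combine. Discontinuation under the tables is mandatory and cutaneous toxicity is the primary outcome, so a DSMB would have to choose between instructions that disagree. The errors run in opposite directions. The first table can stop early without cause by the protocol's own standard. The nodal table lets patients continue where the adjacent text would close the cohort.

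**Working it through.** **Inputs.** The 20% maximum, the 16-of-80 limit and both tables come from the two monitoring sections. The cohort sizes of 50 and 30 come from Data Collection.

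**What the limit means.** In rows 3 to 12 of the first table the printed proportion is the number after the less-than sign divided by n: 3/3 = 100%, 4/5 = 80%, 6/12 = 50%. So the limit of fewer than 7 means a stop at 7.

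**Reproducing rows 3 to 12.** Exact (Clopper-Pearson) 95% limits reproduce the printed ones to rounding, with one exception. For 6/11 the exact interval is 23.4% to 83.3%, and the table prints an upper limit of 93%. In each of these rows the stopping count is the smallest whose exact lower limit exceeds 20%.

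**The last row.** Proportion = 7/n.

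| n | 7/n | Exact 95% CI |
|---|---|---|
| 13 | 53.8% | 25.1% to 80.8% |
| 15 | 46.7% | 21.3% to 73.4% |
| 16 | 43.8% | 19.8% to 70.1% |
| 34 | 20.6% | 8.7% to 37.9% |
| 35 | 20.0% | 8.4% to 36.9% |
| 36 | 19.4% | 8.2% to 36.0% |
| 50 | 14.0% | 5.8% to 26.7% |

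The label is false for n = 35 to 50, which is 16 of the 38 totals in the row. The criterion behind rows 3 to 12 (lower limit above 20%) is lost earlier: with 7 events it holds only for n = 13 to 15. Reading the rule as a stop at 8 events would contradict rows 3 to 12, and the label would still fail for n = 40 to 50 (8/40 = 20.0%).

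**Against 16 of 80.** More than 16 means 17 or more (17/80 = 21.25%).

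- *Tables by cohort.* The end points 50 and 30 match the planned yields. At most 6 + 6 = 12 events (15% of 80) can occur with neither limit reached. If the nodal cohort closes at 7 and the other continues, the most is 7 + 6 = 13. Both are below 17.
- *First table pooled.* There is no limit for patients 51 to 80. At most 6 events can have occurred by patient 50, so reaching 17 needs at least 17 − 6 = 11 of the last 30 (36.7%). This is not a strict contradiction, but the last 30 patients have no continuous limit.

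**Nodal text against nodal table.** The smallest count above 20% is floor(n/5) + 1. At n = 13 this is 3 events (23.1%), while the table stops at 7 (53.8%). The table allows 6 events from n = 13 (46.2%) to n = 29 (20.7%), all above 20%. Over n = 3 to 30, text and table give the same count only at n = 30 (7 events; 6/30 = 20.0% does not exceed 20%).

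**Stopping probabilities.** These come from an exact binomial recursion for a 50-patient cohort, with rows 3 to 12 as printed, a stop at 7 from n = 13, and a look after every patient from n = 3. The true rates are assumed. The last column is the simple binomial probability of 17 or more of 80 at full enrolment.

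| True rate | Stop by n = 34 | Stop by n = 50 | First reached at n = 35–50 | 17 or more of 80 |
|---|---|---|---|---|
| 10% | 4.94% | 23.03% | 18.09 points | 0.2% |
| 15% | 24.30% | 63.91% | 39.60 points | 8.4% |
| 20% | 53.58% | 89.67% | 36.09 points | 43.4% |

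**The case against.** The strongest reply is that a cap tighter than 20% protects patients, so the only demonstrable error is a label. A loose overall ceiling behind a tighter continuous limit is redundant rather than contradictory, and the protocol uses different verbs for the two (suspend, discontinue). In the nodal section, a literal reading of the text would close the cohort at 1 of 3, so the table is probably meant as the working form of the 20% target. The note about the trial stopping sits under a table headed for nodal patients only. The 6/11 figure may be a misprint and changes no stopping count. The SAP, dated 2021, reports 75 included cases in the past tense, so an early stop is no longer a live risk.

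The assumed rates may also be high. The protocol's Background cites under 1% Grade 3 cutaneous toxicity in the institution's own 25-fraction series. The same recursion gives a stop by n = 50 of 0.07% at a true 3%, 1.2% at 5% and 5.9% at 7%.

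Much of this is fair as to size. If the true rate is a few percent, the mislabelled range hardly matters; but that series used a different fractionation, and the protocol itself plans for rates up to 20%. The readings offered for the nodal text and the 16-of-80 limit are plausible, but the protocol states none of them. The point about the lower confidence limit enlarges the problem: by the table's own criterion, stops at n = 16 to 34 are not evidence of a rate above 20% either. That the SAP reports completed data lessens the practical risk but leaves the protocol text wrong.

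**Conclusion.** The concern holds. The stated property of a mandatory stopping limit is false at 16 of the 38 totals it covers, with observed rates at the stop running from 20.0% down to 14.0%. The skin limits in the two monitoring sections are not reconciled under either reading of the first table. The nodal text and table agree at one total only, n = 30, and the text and the note under the table differ on whether the nodal cohort or the whole trial stops.

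The label error and the nodal mismatch are plain arithmetic; the latter takes the more-than-20% text literally. The conflict with 16 of 80 depends on the reading: under the cohort reading the limit cannot be reached while both cohorts are open, and under the pooled reading there is a gap after patient 50. The stopping probabilities assume independent patients, immediate assessment and the illustrative true rates shown. The 6/11 upper limit is a separate, minor error.

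**What to change.** The sponsor and DSMB should reconcile the 13-to-50 row, its label, the 16-of-80 sentence, the nodal text and the nodal skin column so that they express one stated rule. Which limit governs is for them to decide; none is proposed here. The revised text should:

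- say whether the first table covers breast-only patients or all patients, and give a limit for every total up to the planned size;
- state the criterion that generates the limits, and apply it throughout or explain where it changes;
- say whether reaching a nodal limit closes the nodal cohort or the whole trial;
- correct the 6/11 upper limit to 83%;
- report the stopping probabilities of the reconciled rule over a range of true rates, including low ones.

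The cost is protocol wording and recomputed tables, with no extra patients or procedures. If monitoring is already complete, the report should state which rule was actually applied.
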